## Ethics consideration

The study was conducted using human trials, patients with acute stroke treated in RSHS. The observation is a non-invasive procedure that is relatively safe to administer. The description of research ethics is as follows:

1. The research will be submitted to the Ethics Committee and obtain *Ethical Approval*.
2. The research began after obtaining a research permit from the hospital
3. All subjects were given an explanation of the purpose, benefits, and work of the research including the subject's discomfort.
4. Subjects who are willing to participate in the research are asked to sign a letter of consent to participate in the research or *informed consent*.
5. All data and information of the subject are kept confidential.

## Dummy Table

Table 2. Dummy Table

Variable	In Hospital				Follow Up			Difference in change at 3 months
	3 days	Discharge	P-Value	1 Months	2 Months	3 Months	P-Value	
MMT score								
FMA-UE score								
Contraction								
Length of contraction								
Amplitude								

Note: For numerical data, the p value is tested using the paired T test if the data is normally distributed and the alternative Wilcoxon test if the data is not normally distributed. Then, to compare numerical variables between pairs of more than two groups using the repeated ANOVA test if the data is normally distributed and the alternative Fredman test. The significance value is based on a p value of <0.05. The \* sign indicates a p value <0.05, meaning it is significant or statistically significant.

Table 3. Characteristic Table

Variables	p-Value
Sex	
Women	
Men	
Age	
Length of stay	
Stroke diagnosis	
Ischemic stroke	
Haemorrhagic stroke	
Stroke side	
Right hemisphere	
Left hemisphere	
Dominant Hand	
Right	
Left	
Stroke severity	
Minor stroke	
Moderate stroke	
Moderate to severe stroke	
Severe stroke	
Stroke risk factor	
Hypertension	
Diabetes Mellitus	
Heart disease	
Dyslipidemia	
Smoking	
Recurrent stroke	
Yes	
No	

Note: categorical data is presented in number, frequency, and percentage, while numerical data is presented in mean, median, standard deviation, and range.

## Operational Definition

Table 4. Operational Definition of Research

Research Variables	Operational Definition	Measuring Instrument	Result	Measurement Scale
Sex	Sex corresponds which stated on the valid ID card	ID card Family card	Male Female	Nominal
Age	The age limit is stated in years according to the last birthday	ID card Family card	Years	Numerical
Length of stay	Clinical metric that measures the length of time elapsed between a patient's hospital admittance and discharge	Medical record	Days	Numerical
Stroke diagnosis	Acute episode of focal or global neurological dysfunction that persists for more than 24 hours	Medical record and imaging result (CT-Scan, MRI)	Stroke Ischemic Stroke Hemorrhagic	Categorical
Recovery upper motor function in stroke	Improvements of upper extremity motor function, occur in the first few week post-stroke, often reaching a relative plateau after 3 months	FMA-UE	$\leq 25$ : severe 26-45 : moderate 46-66 : mild	Categorical
Stroke side	Hemisphere (side) of blood cannot flow to in the brain	Medical record and imaging result (CT-Scan, MRI)	Right hemisphere Left hemisphere	Categorical
Dominant hand	Individual's preferential use of one hand	Medical record	Right Left	Nominal
Stroke severity	The extent of the impact caused by a stroke	NIHSS score	1-4 : Minor stroke 5-15 : Moderate stroke	Categorical

Stroke risk factor	The subject's risk factors for stroke	Medical record	15-20 : Moderate to severe stroke 21-42 : Severe stroke Hypertension Diabetes Mellitus Heart disease Dyslipidemia Smoking	Nominal
Recurrent stroke	The subject has had their brain deprived of oxygen at least twice, increasing the chances of possible damage to the brain	Medical record and imaging result (CT-Scan, MRI)	Yes No	Nominal
MMT score	Physical exam to testing muscle strength. Scoring use a five-point scale defined as normal, good, fair, poor, trace and zero	Medical record	0-5	Categorical
FMA-UE score	Stroke-specific assessment tool to assess motor functioning, balance, sensation and joint functioning. Comprises 33 items related to the movements of proximal and distal upper extremity. The maximum motor performance score is 66 points	Medical record	≤25 : severe 26-45 : moderate 46-66 : mild	Numerical
Electrical activity deltoid muscle	Electrical activity of the deltoid muscle recorded with a sEMG machine during muscle contraction	Flexcomp Infiniti sEMG	
 
• Contraction (number/minute)
 
• Length of contraction (millisecond)
 
• Amplitude (mV)
 
• Contraction (number/minute)
 
	Numerical
Electrical activity biceps muscle	Electrical activity of the biceps muscle recorded with a sEMG	Flexcomp Infiniti sEMG	
 
• Contraction (number/minute)
 
	Numerical

	machine during muscle contraction		
Electrical activity triceps muscle	Electrical activity of the triceps muscle recorded with a sEMG machine during muscle contraction	Flexcomp Infiniti sEMG	
 
Length of contraction (millisecond)
 
Amplitude (mV)
 
Contraction (number/minute)
 

Electrical activity wrist flexors muscle	Electrical activity of the wrist flexors muscles recorded with a sEMG machine during muscle contraction	Flexcomp Infiniti sEMG	
 
Length of contraction (millisecond)
 
Amplitude (mV)
 
Contraction (number/minute)
 

Electrical activity wrist extensors muscle	Electrical activity of the wrist extensors muscles recorded with a sEMG machine during muscle contraction	Flexcomp Infiniti sEMG	
 
Length of contraction (millisecond)
 
Amplitude (mV)
 
Contraction (number/minute)
 

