## Sample Size Determination

Samples are taken from research subjects that meet the inclusion criteria.

The sample size to test the pair averages then the large determination of the sample, carried out on the basis of statistical calculations by setting the 95% confidence level of the two-way hypothesis and the power test 95%.

Sample determination for categorical numerical analytical research pairs using the formula:

$$n_1 = n_2 = \left( \frac{(Z_\alpha + Z_\beta)S}{X_1 - X_2} \right)^2$$

Where:

$Z_\alpha$  = alpha standard deviation

$Z_\beta$  = beta standard deviation

$S$  = combined standard deviation.

$X_1 - X_2$  = average minimal difference that is considered significant

Type I error is determined as 5%, hence two-ways hypothesis  $Z\alpha = 1,96$

Type 2 error determined as 5%, hence  $Z\beta = 1,64$

Based on the formula, the value is entered into the sample size formula as follows:

$$n_1 = n_2 = \left( \frac{(Z_\alpha + Z_\beta)S}{X_1 - X_2} \right)^2$$

$$n_1 = n_2 = \left( \frac{(1,96 + 1,64) * 1}{1} \right)^2$$

$$= 12,96 \approx 13$$

The minimum sample size for the pre-post test group is 13 people. The minimum number of samples required is 13 samples. The minimum sample number is added to the 10% possibility of sample exclusion so that the minimum sample size is  $13 + 1.3 = 14.3 \approx 15$  samples.

According to Gay and Diehl (1992), the sample must be as large as possible. This opinion assumes that the more samples taken, the more representative they will be and the results can be generalized. The sample size depends on the type of research:

1. The research is descriptive, so the minimum sample = 10% of the population
2. Correlational research, minimum sample is 30 units
3. Comparative causal research, the sample is 30 units per group
4. Experimental research, the minimum sample is 15 units per group

Based on the opinion of Gay and Diehl (1992), the minimum sample for this study for comparative analysis is 30 people. Based on the formula above, the minimum sample size for this research is adequate, so the minimum sample size is 30 samples.

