## **Data Analysis**

Before data analysis is carried out, the data is checked for completeness and accuracy, tabulated, coded, and entered into the computer. The next data analysis aims to describe the dependent and independent variables so that it can help further analysis in more depth. Apart from that, descriptive analysis is also used to determine the characteristics of the research subjects, who are the research samples.

Data analysis to see an overview of the proportions of each variable that will be presented descriptively can be broken down into descriptive analysis and hypothesis testing. Numerical scale data such as age and others are presented with a mean and standard deviation, a maximum value, and a minimum value. The sample characteristic data in the form of categorical data is presented in a frequency distribution table. Data is recorded in the research form that has been created, then editing, verification, coding, and data entry are carried out, and then data analysis

is carried out. Statistical analysis according to research objectives and research hypotheses Data are presented as percentages (%) for categorical variables and mean  $\pm$  standard deviation (SD) for continuous variables. Statistical analysis begins with this normality test aims to find out whether the data is normally distributed or not. The statistical test used to test the data is normally distributed or not, with Shapiro Wilks (because n is less than 50). Numerical variables between pairs of two groups is compared using the paired T test if the data is normally distributed and the alternative Wilcoxon test. Numerical variables between pairs of more than two groups is compared using the repeated ANOVA test if the data is normally distributed and the alternative Fredman test. The McNemar and Marginal Homogeneity tests are used for paired categorical data. The significance of statistical test results is determined based on a p value of  $<0.05$ .

The data obtained was recorded in a special form and then processed using the SPSS version 24.0 for Windows program.

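### Recovery, the outcome of the research question, is defined as improvement but recorded as a single-visit FMA-UE severity band, and the plan contradicts itself on whether the band or the numeric score answers the question

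*Combined protocol and SAP*

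**What the plan says.** The Research Question, Study Objective and Hypothesis sections all ask whether sEMG parameters predict recovery of upper-extremity motor function. Only one row of the plan defines that variable, the recovery row of Table 4 (Operational Definition). Its definition is "Improvements of upper extremity motor function, occur in the first few week post-stroke, often reaching a relative plateau after 3 months". Its instrument is FMA-UE, its result is severe (25 or less), moderate (26-45) or mild (46-66), and its scale is categorical.

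A later row of the same table describes the FMA-UE score: "Comprises 33 items related to the movements of proximal and distal upper extremity", with a maximum of 66. It lists the same three bands as the result but gives the scale as numerical.

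Elsewhere the plan uses the score. Study Variable lists it as a dependent variable and does not list recovery. Outcome Measures names it at five visits. Table 2 (Dummy Table) has an FMA-UE row by visit with a final column for the change at 3 months.

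Data Analysis chooses tests by data type: paired t or Wilcoxon, and repeated-measures ANOVA or Friedman, for numerical data. For the rest, "The McNemar and Marginal Homogeneity tests are used for paired categorical data". No variable is assigned to those last two tests.

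**The concern.** The definition and the measurement in the recovery row describe different things. Improvement needs two visits and a rule for comparing them. A severity band needs one visit and says where the patient stands.

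The scale label also matters, because Data Analysis picks the test from the data type. One instrument carries two labels, so two analysts who both follow the plan could analyse the key outcome in different ways.

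What is at stake is the meaning of the study's only stated outcome. If the band is used, a patient can gain many points without any recorded change, while another gains one point and moves up a level. The protocol takes particular interest in patients with an MMT of 0. Many of them would plausibly start low in the severe band, the widest of the three, where the largest gains can go unseen.

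**Working it through.** **1. The plan's own figure.** Sample Size Determination sets two-sided alpha at 5% (Z = 1.96), beta at 5% (Z = 1.64), S = 1 and a difference of 1:

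n = ((1.96 + 1.64) × 1 / 1)² = 3.60² = 12.96, so 13.

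This agrees with the text: "The minimum sample size for the pre-post test group is 13 people". The 10% allowance gives 13 + 1.3 = 14.3, so 15. The final 30 comes from a rule of thumb. S and the difference have no unit and are tied to no outcome, so the calculation rests on neither the band nor the FMA-UE score. Banding cannot lower a power figure that was never attached to it.

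**2. Largest gain hidden by a band** (upper limit minus lower limit, from the cut-points in Table 4):

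- severe: 25 − 0 = 25 points
- moderate: 45 − 26 = 19 points
- mild: 66 − 46 = 20 points

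The smallest gain that changes the band is 1 point (25 to 26, or 45 to 46).

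**3. Share of gains that leave the band unchanged.** Assumption: whole-number start scores spread evenly over every value from which the gain is possible.

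| Gain | Starts that stay in band | Possible starts | Share |
|---|---|---|---|
| 5 | 21 + 15 + 16 = 52 | 62 | 84% |
| 10 | 16 + 10 + 11 = 37 | 57 | 65% |
| 15 | 11 + 5 + 6 = 22 | 52 | 42% |
| 20 | 6 + 0 + 1 = 7 | 47 | 15% |

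**4. What banding could cost in power: an illustration only.** The documents give no FMA-UE standard deviation, expected gain or correlation with sEMG. The assumed inputs are n = 30; a two-sided 0.05 Spearman test of one sEMG predictor; baseline mean 20-35 with SD 15-18; mean gain 12-15 with SD 10; and scores rounded and kept within 0-66. Ranges run over three baseline-and-gain settings, 2,000 simulated studies each.

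If sEMG tracks the *change* in FMA-UE:

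| True correlation | Change in points | Change in band |
|---|---|---|
| 0.4 | 0.45-0.53 | 0.20-0.28 |
| 0.5 | 0.64-0.75 | 0.26-0.41 |
| 0.6 | 0.82-0.92 | 0.35-0.55 |

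Within each setting the loss is about 25 to 47 percentage points. Among simulated patients who gained at least 5 points, 37% to 44% did not move up a band. At a correlation of 0.5, the band at 3 months alone has power 0.20-0.28 and the numeric 3-month score alone 0.24-0.31. Under this model, then, a numeric score without the 3-day value does little better than the band.

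If sEMG instead tracks the *3-month score* (assumed mean 20-45, SD 15-20; 2,500 studies each), banding costs less. At a correlation of 0.5, power falls from 0.75-0.78 to 0.60-0.71. Over all three correlations the loss is about 5 to 15 points.

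**The case against.** The best defence is that the numeric score looks like the planned outcome. Study Variable and Outcome Measures name it, and Table 2 tabulates it by visit with a change column. The note to Table 2 names only tests for numerical data. The examination form in Lampiran 1 records an FMA-UE score at all five assessments, and the sheet in Lampiran 4 totals to 66. The banded recovery variable appears in no results table. This stands, and it limits the point: information is lost only if the recovery row is followed.

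A reader might infer three stronger things that the documents do not support.

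- *That recovery will be tested by McNemar or marginal homogeneity.* Data Analysis assigns neither test to a variable. McNemar takes paired binary data and could not take three levels. MMT is also labelled categorical in Table 4, so these tests have another possible user.
- *That a one-point move across a cut counts as recovery.* No rule equates a change of band with recovery. The defect is that no rule exists.
- *That the study as planned loses a known amount of power.* No predictor-outcome analysis is specified in bands or in points, and the figures in step 4 rest on assumed inputs.

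Table 2 still does not settle the matter. It describes change across visits, does not call that change recovery and does not link it to sEMG. The one row that defines recovery says categorical, so Table 2 adds to the contradiction.

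**Conclusion.** The point holds as a contradiction in the outcome definition, and the recovery row is wrong as written. This conclusion needs no assumption: the row says improvement, records a state, and conflicts with the FMA-UE row of its own table and with three other sections on the form of the outcome.

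Its size in points is exact under the plan's cut-points: gains of up to 25, 19 or 20 points can be invisible. The 65% and 42% shares for 10- and 15-point gains rest on evenly spread start scores. The size of any power loss is not established. It ranges from about 5 to 47 percentage points over the assumed models, and arises only if the band is what is analysed. The stated sample sizes of 13, 15 and 30 are unaffected.

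**What to change.** Change the recovery row of Table 4 to the numeric FMA-UE score (0-66), scale numerical, with recovery assessed from the 3-day visit to the 3-month visit. State the analysis in Data Analysis as:

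FMA-UE at 3 months = a + b × FMA-UE at 3 days + c × sEMG parameter at 3 days,

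with c as the quantity that answers the research question. Name the sEMG parameter and muscle in advance, since three parameters on five muscles give 3 × 5 = 15 candidates.

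Simple change in points from 3 days to 3 months is an acceptable alternative and matches the change column in Table 2. The covariate form is preferred because possible change depends on the start: a patient at 60 can gain at most 66 − 60 = 6 points.

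Remove the bands from the result column of the FMA-UE score row, or mark them as descriptive, so that both rows agree. Report the bands by visit for description only.

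The cost is a wording change to Table 4 and Data Analysis, slightly more analysis work, and one degree of freedom for the covariate (with 30 complete patients, 27 residual degrees of freedom instead of 28). No new data, visits or patients are needed.

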## Outcome Measures

The investigator assessed the outcome measures. The outcome measures are MMT score, FMA UE score, sEMG parameters (contractions, length of contraction, and amplitude). It is measured at 3 days of stroke onset, the day of discharge from hospital, 1 months, 2 months and 3 months after stroke onset.

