## 3. Processing phase

Processing the signal is proses that the raw signal has to be prepared so that it can be easily observed and analysed. The type of processing will depend on the type of analysis we wish to make from the trace.

Many different quantitative parameters can be evaluated from sEMG data such as number of contractions, contraction magnitude, contraction duration, presence of synergistic activations, evaluations of spasticity, or measures of voluntary vs. involuntary contractions.

Surface EMG's signal parameters related to muscle contraction include time analysis and amplitude analysis. The time analysis includes length of contraction. The length of contraction is a parameter for evaluating the period of muscle contraction from manually identified start until end times.

Papazian et al. successfully used the number of contractions, maximum amplitude, median amplitude, and duration from the manually identified start and end times the contractions to measured muscle activity in acute stroke patients. They also evaluated the correlation between the number of contractions, amplitude, and duration. The participants with an MMT of 0, individuals with more contractions had greater maximum amplitude and longer duration contractions.

The primary advantage of sEMG along with its non-invasive nature, is that the signals are relatively straightforward to record and analyse (with some basic signal processing knowledge). It also provides an estimate of the overall activity of a muscle or group of muscles in contrast to the more selective nature of intramuscular recordings.

Surface EMG, however, is only suitable for recording from superficial muscles and is not appropriate for recording deep muscle activity. Recording from small muscles without contamination from surrounding muscles can be difficult and signals can be prone to cross-talk, particularly over regions where there is substantial subcutaneous fat.

Surface EMG's signal has complex nature, and the huge number of variables upon which it depends, so it is important to critically analyse the signal knowing the effects of these variables on its properties. Several years now, an

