## Research Work Procedure

This research collaborates with the ITB engineering team and the procedure of research is carried out as follows:

1. Selection of subjects according to the criteria of inclusion and exclusion.
2. Research subjects are given an explanation of the research procedure as well as signing informed consent to participate the research.
3. Research subjects who agree to participate in the study sign the informed consent
4. Data registration of the examination form in the medical record
5. Examination of vital signs to see contraindications for further examination. The subjects used a pulse oximetry during the subsequent examination.
6. Upper extremity function assessment is carried out using MMT and FMA UE.
7. Electrical activity recording of deltoid, biceps, triceps, wrist flexors and wrist extensors muscles is performed using sEMG is carried out as follows:
  - a. The subjects are positioned sitting at 60-90 degrees during recording. Put an arm pillow below the impaired hand.
  - b. Preparation of the sEMG (Biograph Infinity) machine for observation the contraction of muscles.
  - c. Clean the skin first using alcohol swab to reduce skin impedance

- d. Ground electrodes are attached to the bone structures in the elbow in the impaired side (olecranon)
- e. Electrodes with diameter 50 mm are placed in impaired side at the anterior deltoid, long head of the biceps, lateral head of the triceps according to the Surface Electromyography for the Noninvasive Assessment of Muscles (SENIAM) guidelines standard placement procedures (Figure 5). Bony anatomical landmarks of the medial and lateral humeral epicondyles were used for standard placement of the subsequent electrodes the wrist flexor and extensor muscle groups, as SENIAM does not offer placement guidelines for these muscles

Figure 5. Electrodes/sensor placement

- f. Each muscle is examined by positioning two electrodes on it, separated by a distance of one or two centimeters
- g. The electrodes are fixed when the electrical activity is clearly visible on the monitor with minimal noise

- h. Muscle signal data were collected for 30 minutes
  - i. During 30 minutes, the subjects do the protocol activity (Figure 6) as describe, for subjects with MMT 0, the researcher then performed a passive range of motion:
    - 00:01:00 (shoulder flexion)
    - 00:02:00 (rest)
    - 00:03:00 (shoulder flexion)
    - 00:04:00 (rest)
    - 00:05:00 (shoulder flexion)
    - 00:06:00 (rest)

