    - 00:07:00 (elbow flexion)
    - 00:08:00 (rest)
    - 00:09:00 (elbow flexion)
    - 00:10:00 (rest)
    - 00:11:00 (elbow flexion)
    - 00:12:00 (rest)
    - 00:13:00 (elbow extension)
    - 00:14:00 (rest)
    - 00:15:00 (elbow extension)
    - 00:16:00 (rest)
    - 00:17:00 (elbow extension)
    - 00:18:00 (rest)
    - 00:19:00 (wrist flexion)

- 00:20:00 (rest)
- 00:21:00 (wrist flexion)
- 00:22:00 (rest)
- 00:23:00 (wrist flexion)
- 00:24:00 (rest)
- 00:25:00 (wrist extension)
- 00:26:00 (rest)
- 00:27:00 (wrist extension)
- 00:28:00 rest
- 00:29:00 (wrist extension)
- 00:30:00 (rest)

[figure not shown]

Figure 6. The five movements tested in the experimental setting. Shoulder flexion (a), elbow flexion (b), elbow extension (c), wrist flexion (d), wrist extension (e).

j. The electrodes are released and the scratch area is checked to see if there are any signs of irritation

- k. The subjects are informed that the data collection has been completed, the sEMG engine cleaned up.
8. Surface EMG's signal recording results in digital form were submitted to the ITB Engineering team for the processing of the signal. The results of the electrical activity features of the muscle are contraction, length of contraction and amplitude will be analyzed.
9. All assessment (MMT, FMA UE and sEMG) is carried out at 3 days of stroke onset, the day of discharge from hospital, 1 month, 2 months and 3 months after stroke onset.

[figure not shown]

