## Penilaian dan Pemeriksaan MMT, FMA-UE dan sEMG

No	MMT Score	FMA-UE Score	sEMG				
			Deltoid	Biceps	Triceps	Wrist flexors	Wrist extensors
Pemeriksaan 1			K: LK: A:	K: LK: A:	K: LK: A:	K: LK: A:	K: LK: A:
Pemeriksaan 2			K: LK: A:	K: LK: A:	K: LK: A:	K: LK: A:	K: LK: A:
Follow Up 1			K: LK: A:	K: LK: A:	K: LK: A:	K: LK: A:	K: LK: A:
Follow Up 2			K: LK: A:	K: LK: A:	K: LK: A:	K: LK: A:	K: LK: A:
Follow Up 3			K: LK: A:	K: LK: A:	K: LK: A:	K: LK: A:	K: LK: A:

\*MMT: manual muscle testing, FMA - UE: Fugl Meyer Assessment – Upper Extremity, sEMG : surface electromyography, K: kontraksi, LK: lama kontraksi, A: amplitudo

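### The plan gives sEMG and the observer-rated FMA-UE to the same role and one shared form, and specifies no masking of the FMA-UE scorer or the signal processors

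*Combined protocol and SAP*

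**What the plan says.** - **Who assesses.** Outcome Measures states: "The investigator assessed the outcome measures". The next sentence lists what that covers: "The outcome measures are MMT score, FMA UE score, sEMG parameters (contractions, length of contraction, and amplitude".
- **When.** Research Work Procedure, step 9: "All assessment (MMT, FMA UE and sEMG) is carried out at 3 days of stroke onset, the day of discharge from hospital", and again at 1, 2 and 3 months. That makes five visits.
- **Order within a visit.** Step 6 comes first: "Upper extremity function assessment is carried out using MMT and FMA UE". The sEMG recording is step 7.
- **What can be seen during recording.** Step 7g: "The electrodes are fixed when the electrical activity is clearly visible on the monitor with minimal noise". Under step 7i, an MMT score of 0 means that the researcher moves the limb passively.
- **Signal processing.** Step 8: "Surface EMG's signal recording results in digital form were submitted to the ITB Engineering team for the processing of the signal". The step does not say what identifies a file, what clinical information goes with it, or when the processed values come back.
- **Recording of results.** The examination form (Lampiran 1) has one table, titled "Penilaian dan Pemeriksaan MMT, FMA-UE dan sEMG". It has a row for each of the five visits and columns for MMT, FMA-UE and three sEMG parameters in five muscles. Step 4 places the examination form in the medical record. The FMA-UE items have their own sheet (Lampiran 4), with an examiner field and no sEMG field.
- **Masking.** No section specifies any, and none separates the assessors.

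**The concern.** Under the research question and hypothesis, sEMG is the predictor. Under Operational Definition (Table 4), FMA-UE is the measure of recovery. FMA-UE items are scored 0, 1 or 2 by watching the movement, so the total depends partly on judgement. The recovery categories divide at 25/26 and 45/46, so a single point can move a patient from one to another.

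Two routes of contamination are open. A scorer who knows that a patient's earlier sEMG looked strong may rate borderline items more generously later, which would make sEMG look predictive when it is not. In the other direction, a signal processor who knows that a recording is from 3 months, or knows the clinical score, may expect more or longer contractions and make choices accordingly. The second route does not need an analysis linking sEMG to FMA-UE. It would affect the changes over time in sEMG that Data Analysis and the Dummy Table already plan to test.

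**Working it through.** The plan has no figure on this point to reproduce. Its sample-size arithmetic does not involve masking and is unaffected. The check is therefore a reading of the sections side by side.

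**1. What the step order protects.** FMA-UE (step 6) precedes sEMG (step 7) at every visit. For a patient with no missed visits, the sEMG sessions completed before each FMA-UE are:

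| FMA-UE at | Earlier sEMG sessions |
|---|---|
| Day 3 | 0 |
| Discharge | 1 |
| 1 month | 2 |
| 2 months | 3 |
| 3 months | 4 |

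No score can be influenced by the same visit's recording. Only day 3 is free of all earlier recordings, and the 3-month score has the most behind it.

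**2. What the scorer can know.** Step 7g establishes that the live trace is seen. The processed values are a separate matter. The form has 3 parameters × 5 muscles = 15 sEMG cells per visit, so up to 4 × 15 = 60 earlier cells could be filled by the 3-month visit. Whether they are filled depends on when the engineering team returns values, which is not stated. Anything between 0 and 60 is consistent with the text.

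**3. What the processors can know.** Step 8 names only digital recordings. It neither says that visit or clinical scores travel with the files nor requires their removal. The Dummy Table compares contraction, contraction length and amplitude between day 3 and discharge and across 1, 2 and 3 months. Knowledge of the visit is therefore knowledge of the factor being tested.

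**4. Size (hypothetical only).** No bias can be derived from the documents. Suppose that the true sEMG–FMA-UE correlation is 0 and the scorer shifts FMA-UE by k SD per SD of earlier sEMG, where k is an assumption. The apparent correlation is r = k/√(1 + k²). With n = 30 and m = atanh(r) × √27, the two-sided 5% rejection rate is 1 − Φ(1.96 − m) + Φ(−1.96 − m):

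| k (assumed) | r | m | False-positive rate |
|---|---|---|---|
| 0 | 0 | 0 | 5% |
| 0.1 | 0.10 | 0.52 | 8% |
| 0.2 | 0.20 | 1.03 | 18% |
| 0.3 | 0.29 | 1.54 | 34% |

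These rates belong to a correlation test that is not in the written analysis, and they should not be quoted as properties of this study. They show only that, if such a test were added, modest shifts would matter at this sample size.

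**The case against.** The strongest reply is that the documents are mostly silent rather than wrong, and that several stronger readings do not follow from them. Much of this stands.

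- A reader might infer that FMA-UE is scored on a sheet already showing all earlier sEMG results. The documents do not support that. Items are scored on Lampiran 4, which has no sEMG field, and the shared form has only one cell per visit for the score. Processed values might not be entered until after the last visit.
- A reader might infer that the engineering team knows the clinical scores. The text supports only that no masking is specified.
- A reader might infer that one person does everything. Outcome Measures names a role, and the examiner field on Lampiran 4 leaves the number of people open.
- A reader might infer that contraction length will be marked by hand, from the phrase "period of muscle contraction from manually identified start until end times". That phrase is in the literature review and describes earlier work. The study's own definition gives only the unit, and the processing method is left to the engineers.
- The Data Analysis section plans paired tests, repeated-measures tests and tests for paired categories. It plans no correlation or regression, so the hypothetical error rates correspond to no planned test.
- The only knowledge route that the documents establish is the live trace, and the fix leaves it open.

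The core remains. The same role covers predictor and outcome over five visits, the results share one form, and nothing prevents later FMA-UE scores from being given with knowledge of earlier sEMG. The step order answers this within a visit but not across visits.

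**Conclusion.** The concern holds as an unprotected exposure, not as demonstrated bias. It affects FMA-UE from discharge onward, including the 3-month score on which a claim about recovery would rest. It also affects the planned within-patient sEMG comparisons if the processors know the visit. Its size is unknown.

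The conclusion rests on two things: that sEMG is the predictor, as the hypothesis says (Study Variable lists both sEMG and FMA-UE as dependent), and that no masking is specified in the text supplied, where the research-flow figure is not shown. The matter deserves action because masking cannot be restored once scores have been given and the remedy costs almost nothing. It is a cheap improvement.

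**What to change.** No new staff, visits or patients are needed.

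1. Send recordings to the engineering team under a random code, without visit, MMT or FMA-UE. Keep only the movement labels and an active/passive flag, which processing needs.
2. Have the engineering team hold each patient's processed sEMG values until that patient's 3-month FMA-UE has been scored.
3. Record processed sEMG on a page separate from the MMT and FMA-UE totals on the examination form.

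The protocol should state these rules, together with who scores FMA-UE and what the scorer and the processors may see.

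The cost is a code list, a holding rule and a re-laid form. Masking will be partial: the investigator still sees the live trace, and the passive flag tells the processors that MMT was 0. Both should be reported as limitations. Any figure for the resulting bias should be left out or labelled hypothetical.
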